Study Protocol

Background:

Urinary tract infection (UTI) is a common infection of the urethra, bladder and/or kidneys, commonly associated with symptoms including needing to urinate more frequently and urgently than normal, a painful or burning sensation during or after urination, among others.

Recurrent UTI (rUTI) is defined as experiencing either two or more UTI episodes in six months or three or more in one year. This chronic condition is debilitating, with existing research indicating a significant impact to quality of life and considerable socioeconomic burden. However, the majority of existing research in this area focuses on the causes behind the condition and treatment options while considering antimicrobial resistance, for example. This means that the patient-reported experience of what it means to live with rUTI is often neglected.

Clinical diagnosis of a UTI often requires positive urine dipstick or urine culture results. However, it is understood that these tests may not be consistently reliable. This can lead to missed diagnosis, and potentially missed treatment, of UTI episodes, in turn leading to prolonged symptoms and feelings of patient dissatisfaction.

A patient-reported outcome measure (PROM) is a measurement tool which can be used to gain insight into a patient's own perspective on certain aspects of their health. For example, a PROM may seek to understand a patient's views on how severe they feel their symptoms are, or how much their condition has interfered with their lifestyle. PROMs are typically designed to be used alongside clinical outcome measures, e.g. urinalysis results, in order to build a more holistic picture of the patient's health and health-related quality of life.

While there are several generic PROMs which effectively measure areas relevant to rUTI, e.g., health-related quality of life (e.g. 36-Item Short Form Survey), there are no existing validated rUTI-specific PROMs. Condition-specific PROMs can be especially useful in gathering information about aspects of health which may be unique to or present differently in the relevant patient population, and it is recommended that they are used as well as generic PROMs. In this study, we aim to develop and validate two new rUTI-specific PROMs: one measuring rUTI symptoms and symptom intensity, and one measuring rUTI impact. Our intention is that these measures could be used to assess effectiveness of treatments and interventions for people living with rUTI.

A crucial element of PROM development is the involvement of patients. This study will ground its development in existing qualitative research of rUTI patient experiences as well as conducting cognitive interviews with rUTI patients to obtain their perspective on whether the PROM questions are appropriate and valid for the population and their experiences of rUTI. Following this, pilot data collection of the PROMs alongside existing standardised measures of contextually relevant health aspects (e.g. pain) will be conducted to perform further statistical validity checks. The cognitive interviewing and piloting of the PROMs may include a mild risk of anxiety or discomfort due to the sensitive nature of some questions and need to reflect on potentially challenging experiences. Participants will maintain the right to withdraw at any point and will be encouraged to seek support from their GP/healthcare professional if needed.

Research Questions:

Primary aims:

1. To develop a patient-reported outcome measure of rUTI symptoms.
2. To develop a patient-reported outcome measure of rUTI impact.

Secondary aims:

1. To validate the rUTI symptom PROM by conducting statistical tests of its internal consistency, test-retest reliability, construct validity and criterion validity.

2. To validate the rUTI impact PROM by conducting statistical tests of its internal consistency, test-retest reliability, construct validity and criterion validity.

Design and Procedure:

An initial rUTI symptom scale and rUTI impact questionnaire have been developed based on existing qualitative research and literature review. The rUTI Symptom Scale includes a UTI-related symptom intensity subscale, and a UTI-pain intensity sub-scale. This PROM is designed to assess symptom intensity over the past 24 hours. The rUTI Impact Questionnaire includes a personal wellbeing subscale (covering psychological wellbeing and sleep/exercise disruption), a social subscale (covering social impact, isolation and anxiety), a work impact subscale, a sexual subscale (covering sexual impact and pain), and a patient satisfaction subscale. This PROM is designed to assess rUTI impact over the past two weeks.

A three-stage methodology will be employed:

(1) Expert screening for content validity

Following ethical approval, these PROMs will be initially screened for content validity by a 6–10 experts in the domain of rUTI and general medicine. Between 6–10 experts in medical fields relevant to rUTI will be required to participate in one-to-one interviews, an appropriate sample size for calculating content validity (Yusoff, 2019). A modified two-stage Delphi methodology will be implemented, obtaining experts' views over two "rounds" in order to reach consensus on item validity via a survey built in REDCap. The second round will take place 28 days after the first.

In the first round, participants will be asked to read the Information Sheet and sign the Consent Form before completing the demographics questionnaire. Then, they will be asked to rate each questionnaire item for relevance within the field of recurrent UTI on a scale of 1 (not relevant at all) to 9 (highly relevant), and for clarity, on a similar scale (1 (not clear at all) to 9 (very clear)). This scaling system is the most commonly used in Delphi studies (McMillan et al., 2016). Participants will also be invited to provide free-text qualitative feedback to justify their ratings. They will also be asked if they have any general comments about each PROM. Participants will be provided with a debrief form at the end, reminding them to look out for their reminder email in 28 days' time with the link to access the second and final part of the study.

In the second round, participants will be asked to do this again, except now being provided with their previous relevance and clarity ratings, the median rating across all expert-scores, and a diverse selection of the free-text comments received in the first round. Participants will be able to retain their original scores or make changes, giving additional free-text responses if desired. In this survey, there will be an updated information sheet, consent form and debrief form. This step will provide us with both content validity and clarity scores as well as qualitative feedback on the measures. This feedback will allow for further refinement of the PROMs before the main participant studies are conducted, as detailed below in steps 2 and 3.

(2) Cognitive interviewing and at-home completion of the rUTI Symptom PROM:

The same procedure will apply for the rUTI impact PROM. After completing both questionnaires, the interviewer will thank the participant for their time, provide them with the opportunity to ask any questions, and describe what will happen next in the wider research project and how their feedback will be used. The participant will be provided with the Debrief Form which provides them with recommended links to access support should they need it. This form will also invite participants to contact the researchers should they wish to receive a copy of the final PROMs and/or report.

Due to the personal nature of some questions in both rUTI PROMs and the need for participants to reflect on their experiences of living with their chronic illness, there is a mild risk that participants may experience negative feelings such as anxiety. This is explained in the Information Sheet and will also be explained verbally at the start of the interview, and the participants reminded of their right to withdraw from the study/interview at any point.

After one “round” of cognitive interviews, both the rUTI symptom and impact PROMs will be refined based on findings. A second “round” will then take place with a new set of participants with rUTI, before further refinement ahead of the pilot study.

It is planned that approximately 30 participants will be recruited to participate in cognitive interviews across rounds 1 and 2, as described in the procedure section. A sample size of approximately 30 participants is recommended to sufficiently perform pre-tests of new psychometric questionnaires (Perneger et al., 2015). It is suggested that smaller samples of between 5-15 participants “may fail to uncover even common problems” of misunderstandings and ambiguities in instrument items. In a similar PROM development study to this rUTI study, which developed two new symptom and impact PROMs for endometriosis, recruited a sample of 31 participants for their cognitive interviews, also split across two interview rounds (Gater et al., 2020).

(3) Online pilot of rUTI PROMs and other comparable measures:

To obtain data to perform statistical validity checks of these two new PROMs among comparable other measures, a two-part online survey of adult rUTI patients will then be conducted. Parts 1 and 2, which will be separated by 24 hours which to allow for test-retest reliability assessment, will follow identical procedures (with the exception of Part 1 additionally including a demographics questionnaire). It is planned that a minimum of 132 participants will be recruited to take part in the online PROM data collection stage. A minimum of 100 participants will be

required to complete both parts, based on the COSMIN guidelines (Mokkink et al., 2018) and common practice for conducting exploratory factor analysis (Fabrigar et al., 1999). With an anticipated attrition rate of 25%, based on that found in a study examining retention rates in health outcome measure surveys (Hall et al., 2018), a minimum of 132 participants should be recruited to retain adequate statistical power.

The Part 1 online survey, built in REDCap, will start with a Participant Information Sheet and then Consent Form. Participants who wish to take part will be able to complete this survey virtually, e.g. from home. The Information Sheet is similar to the one used in the cognitive interviewing stage, except the procedure description is updated accordingly. In order to access the main study, the participant will be required to confirm their consent by ticking each item on the Consent Form page and providing an electronic signature. They will then access and complete a Demographics Questionnaire.

The rest of the survey will present a series of questionnaires to the participant. Two will be the new rUTI PROMs which we have developed and refined, and there will also be a number of existing standardised measures which measure similar concepts of symptom intensity and health impact: the symptom severity subscale of the UTI Symptom Assessment (Clayson et al., 2005), Numerical Pain Rating Scale (Jensen & Karoly, 2011), UCLA Loneliness Scale Version 3 (Russell, 1996), Work Productivity and Activity Impairment questionnaire (Reilly et al., 1993), Female Sexual Distress Scale – Revised (Derogatis et al., 2008), Patient Satisfaction Questionnaire Short-Form (Marshall & Hays, 1994), Generalised Anxiety Disorder – 7 (Spitzer et al., 2006), and Patient Health Questionnaire – 9 (Kroenke et al., 2001). It is explained in the Information Sheet that the participant may be asked questions which seem to measure the same thing; this is due to the inherent similarity in some of the measures and the participant should continue to answer all questions in the survey. It is expected that the total survey will take the participants approximately 30 minutes to complete, which is noted in the Information Sheet.

At the end of the survey, the participant will be shown a Debrief Form which provides them with the aforementioned recommended links to access rUTI or mental health support should they need/want it, and reminds them that in 24 hours' time they will receive an email with a link to access and complete the Part 2 survey. The link in this email will be unique for each participant, linking their Part 1 and Part 2 responses in REDCap.

The Part 2 survey, to be completed approximately 24 hours' after Part 1, follows the exact same procedure as in Part 1, with the wording updated in the Participant Information Sheet, Consent Form and Debrief Form to reflect that this is the final part of their participation and no more communication will be required following this step. As in the cognitive interview debrief form, participants will be invited to contact the researchers should they wish to receive a copy of the final PROMs and/or report. The same mild risk of feelings of anxiety in the cognitive interview stage applies here. Similarly, participants will be fully informed of this possible risk and the reasons for the personal nature of the questions asked, as well as their right to stop their participation at any point.

References:

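### At the stated 25% attrition, recruiting 132 gives 99 expected completers, one short of the Protocol's own minimum of 100; the figure consistent with its inputs is 134

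*Protocol*

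**What the plan says.** The sample size for the online pilot is set in the Protocol, Design and Procedure, stage (3), in three steps.

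- **Recruitment:** "It is planned that a minimum of 132 participants will be recruited to take part in the online PROM data collection stage".
- **Completers:** the floor is 100 people, described as "required to complete both parts, based on the COSMIN guidelines (Mokkink et al., 2018) and common practice for conducting exploratory factor analysis".
- **Link between the two:** "With an anticipated attrition rate of 25" per cent, a rate taken from a cited study of survey retention, the Protocol concludes that "a minimum of 132 participants should be recruited to retain adequate statistical power".

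The SAP gives no sample size, attrition rate or power statement for this stage, so nothing there changes or explains the 132.

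**The concern.** The three figures are presented as one derivation: a floor on completers, an attrition rate, and the recruitment number that follows from them. A reader who multiplies them out finds that they do not agree. A team that stops at exactly 132 has followed the recruitment sentence, yet at the planned attrition it expects to finish below the floor set just before it.

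The same sentence says that 132 is needed "to retain adequate statistical power". That wording suggests a power calculation in which 132, or 100, was the answer. The stated basis for the 100 is different: guidance and common practice. What is at stake is whether the stated sample size follows from its own inputs, and whether the reason given for it is the real one.

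**Working it through.** **Inputs, all from Protocol stage (3)**

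- Required completers of both parts: 100 (a minimum)
- Attrition d: 25%
- Recruitment: 132 (a minimum)

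**Step 1. Try to reproduce 132.**

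- Usual inflation, N / (1 − d): 100 / 0.75 = 133.33, rounded up to **134**.
- Common shortcut, N × (1 + d): 100 × 1.25 = 125.

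Neither gives 132. It lies 2 below the first result (2 / 134 = 1.5%) and 7 above the second. It is therefore close to the correct method and is not the product of the shortcut.

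**Step 2. Work forward from the recruitment figure.**

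| Recruited | Expected completers at 25% attrition |
|---|---|
| 132 | 132 × 0.75 = 99.00 |
| 133 | 133 × 0.75 = 99.75 |
| 134 | 134 × 0.75 = 100.50 |

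The smallest number that reaches 100 in expectation is 134.

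**Step 3. Find the attrition rate at which 132 works.**

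1 − 100 / 132 = 0.2424, or about 24.2%. At 24%, 100 / 0.76 = 131.6, which rounds up to 132. So 132 would be right if the working rate had been about 24% and was rounded to 25% in the text. The documents do not say this.

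**Step 4. What one completer is worth.**

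For statistics whose standard error falls with the square root of n, moving from 100 to 99 inflates it by √(100 / 99) = 1.005, or 0.5%.

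As a check on test-retest reliability, take an F-based 95% interval for an ICC from two ratings. Set F = (1 + ICC) / (1 − ICC), divide and multiply F by the 97.5th percentile of the F distribution on (n − 1, n − 1) degrees of freedom, and convert each limit back with (F − 1) / (F + 1). That percentile is 1.4893 at n = 99 and 1.4862 at n = 100. The documents state no expected ICC, so the values below are assumptions.

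| Assumed ICC | 95% CI, n = 99 | 95% CI, n = 100 |
|---|---|---|
| 0.60 | 0.457 to 0.713 | 0.458 to 0.712 |
| 0.70 | 0.584 to 0.788 | 0.584 to 0.788 |
| 0.80 | 0.716 to 0.861 | 0.717 to 0.861 |
| 0.90 | 0.855 to 0.932 | 0.855 to 0.932 |

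Each pair agrees to two decimals. The SAP specifies an absolute-agreement model, whose interval can differ somewhat from this approximation, but the comparison of 99 with 100 would be equally flat.

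**Step 5. Look for the power calculation.**

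No hypothesis, effect size, significance level or target power accompanies the sample size in the Protocol, and none is given in the SAP. The main reliability and validity results in the SAP's Statistical analyses section (factor loadings, Cronbach's alpha, ICCs with 95% confidence intervals, Spearman correlations) are estimates, and no power is attached to any of them.

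**The case against.** The strongest reply is that both numbers are floors. Recruiting more than 132 is permitted, and the requirement of 100 completers stands separately, so a team that kept recruiting until 100 had finished would satisfy both sentences. This stands as a limit on the consequence. It does not rescue 132 as the number derived from 25% attrition, which is how the Protocol presents it.

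A second reply is that 25% may be a rounded version of a rate near 24%, which would make 132 correct. That is possible and cannot be checked from the documents. It affects which correction is right, and so stating the rate actually used is one of the options under the fix.

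A third is that the reference to power is only loose wording, since the same text openly bases the 100 on guidance and practice. That is fair. It makes this a wording correction and not evidence of a missing analysis.

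Two stronger readings are tempting, and the documents support neither.

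- **A reader might infer that the study loses power.** No power was calculated, so none can be shown to be lost, and Step 4 shows that precision is essentially unchanged.
- **A reader might infer that the pilot is more likely than not to miss its minimum.** If each participant completes independently with probability 0.75, the chance of at least 100 completers is 46.7% with 132 recruited. That independence is an assumption the documents do not make, and the figure also treats 132 as a cap. On the same assumption 134 gives 58.5% and still misses about 41% of the time; an 80% chance would need 139. The probabilities therefore say little about the slip itself, which is a gap of one person in expectation.

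**Conclusion.** The point holds as a minor arithmetic error. On the Protocol's own inputs, 132 recruits yield 99 expected completers against a floor of 100, and the consistent recruitment figure is 134. The gap is one expected completer, or two recruits. This rests only on reading the 25% as exact and as applying to everyone recruited, which is how the text uses it. There is no material effect on precision and no demonstrated loss of power. Separately, the phrase about power describes a justification that the documents do not contain; the 100 rests on COSMIN guidance and factor-analysis practice.

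**What to change.** In Protocol stage (3), make one of these changes:

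1. restate the minimum recruitment as 134 in both places where 132 appears; or
2. keep 132 and say that 99 completers are expected at 25% attrition; or
3. keep 132 and state the attrition rate actually used, if it was about 24.2% or lower.

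In the same sentence, replace the reference to adequate power with a statement that the number is meant to retain the minimum of 100 completers.

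The cost is a sentence or two of editing and, under the first option, at most two more online participants. The SAP describes the pilot analyses in the past tense, so recruitment may already be closed. In that case, correct the stated rationale and report the number who actually completed both parts.

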Statistical Analysis Plan:

The below describes the statistical considerations for analysing the data collected in the study, including the specific analytical steps and methods used at each step, and the assumptions tested and verified. Best practice recommendations for the development and validation of new patient-reported outcome measures (PROMs) by the COSMIN initiative were followed throughout (Mokkink et al., 2018; Prinsen et al., 2018).

Stage 1: Expert screening

Best practice for Delphi methodology analysis was followed (McMillan et al., 2016). After Round 1, median relevance and clarity ratings were computed and presented in Round 2 alongside anonymised qualitative feedback. Following Round 2, new median ratings were calculated and analysed in conjunction with all the qualitative feedback. Content validity indices for items (I-CVI) were computed by dividing the number of expert clinicians who scored an item's relevance/clarity as at least four out of six by the total number of expert clinicians (Yusoff, 2019). It was specified a priori that a minimum I-CVI of 0.75 would be required to indicate acceptable consensus of content validity, with a minimum median score of 4 (McMillan et al., 2016; Polit & Beck, 2006). Refinements were made to create second versions of the RUTISS and the RUTIIQ, ready for patient testing in Stage 2.

Stage 2: Cognitive interviews

Guidance by Willis on conducting and analysing cognitive interviews for questionnaire design and appraisal was followed (Willis, 2005; Willis, 2015). Anonymised verbatim transcripts of the interviews were created using speech-to-text software (Otter; <https://otter.ai>) with transcription errors manually corrected. The corresponding portions from every interview transcript for each PROM item were collated to create individual documents for each item containing all feedback pertaining to that question from across the entire sample. Top-down question feature coding was applied to these summaries using the Question Appraisal System (QAS-99) (Willis & Lessler, 1999). The systematic evaluation of every response to each PROM item for both the RUTISS and the RUTIIQ was conducted to identify potential problems, which were corrected based on verbatim quotes and interviewer field notes through collaborative analysis with the entire research team. If there were any uncertainties found in the first round of interviews about whether to include or exclude an item, the item was retained in the second round to gain further feedback. Further versions of the RUTISS and the RUTIIQ were created at this stage and used in the second interview round. The same process was undertaken after this, with an amended version created for pilot testing.

Stage 3: Online pilot testing

Data preparation and assumption testing:

Total scores were calculated for each of the Recurrent Urinary Tract Infection Symptom Score (RUTISS) subscales at Baseline and Test-Retest Assessments. Total scores for the RUTISS as a whole measure were not computed to avoid misrepresenting multidimensional constructs as a single score (Strauss & Smith, 2009). Data collected using the Urinary Tract Infection Symptom Assessment (UTISA) and Numerical Pain Rating Scale (NPRS) were scored according to their standard scoring systems.

The following assumptions were assessed: (1) normality – Shapiro-Wilk $p > .05$, so non-parametric analyses were conducted where applicable; (2) linearity – examination of scatter plots confirmed no violation; (3) multicollinearity – Variance Inflation Factor scores for the target label data as well as possible demographic characteristics were sufficiently close to 1; (4) independence of observations – Durbin-Watson statistic was approximately 2 for each subscale

score; and (5) homoscedasticity – (inspection of the standardised residuals plotted against standardised predicted values confirmed no violation).

Case-wise diagnostics of the subscale scores indicated five possible outliers outside 3SD; however, since these were not measurement errors and could feasibly reflect true variation within the population, they were not removed. Analyses conducted with and without these cases indicated that they had no statistically significant effect on the outcomes ($p > .05$).

Statistical analyses:

Exploratory factor analysis (EFA) was conducted for both the RUTISS and RUTIIQ data. Suitability for EFA was checked through bivariate correlation matrices with coefficients greater than .80 examined for potential multicollinearity (Field, 2013). Preliminary data analyses were undertaken to assess the factorability of the dataset using Bartlett's Test of Sphericity and the Kaiser-Meyer-Olkin Measure of Sampling Adequacy (Yong & Pearce, 2013). Principal Axis Factoring was selected for application above Principal Components Analysis and Maximum Likelihood Analysis to facilitate determination of a latent factor structure (Fabrigar et al., 1999; Yong & Pearce, 2013). Varimax rotation with Kaiser Normalisation was applied to minimise cross-loading of items on factors (Fabrigar et al., 1999). Visual inspection of scree plots determined the retained number of factors, combined with evaluation of eigenvalues exceeding Kaiser's criterion of 1 (Kaiser, 1960; Watkins, 2018). Items with extracted communalities less than .40 were removed, and a minimum factor loading of .40 was defined as acceptable a priori (Fabrigar et al., 1999; Watkins, 2018).

Internal consistency was measured for each finalised post-EFA RUTISS subscale and the RUTISS as a whole measure using Cronbach's alpha (Cronbach, 1951). To assess test-retest reliability, intraclass correlation coefficients (ICC) and their 95% confidence intervals were computed based on a single-rating, absolute-agreement, two-way mixed effects model, as recommended for test-retest reliability analysis of measures intended to demonstrate outcomes at an individual (single-rater) level (Koo & Li, 2016). Construct validity was assessed by computing the level of Spearman's correlation between each RUTISS subscale and the observed UTISA and NPRS scores (Schober et al., 2018).

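### The SAP's expert-panel cut-off is out of six but the protocol's rating scale runs from 1 to 9; if 1-9 was used, the cut-off falls below the midpoint

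*SAP*

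**What the plan says.** **Protocol, Design and Procedure, (1) Expert screening for content validity.** Experts rate relevance "on a scale of 1 (not relevant at all) to 9 (highly relevant") and clarity on a like scale, "1 (not clear at all) to 9 (very clear"). The choice is defended: "This scaling system is the most commonly used in Delphi studies". The second round keeps the same task: "In the second round, participants will be asked to do this again", this time with sight of their own earlier scores, the panel median and selected comments. On panel size: "Between 6–10 experts in medical fields relevant to rUTI will be required to participate". The protocol gives no I-CVI or median threshold.

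**SAP, Stage 1: Expert screening.** The I-CVI numerator is the number of experts who scored an item's "relevance/clarity as at least four out of six"; the denominator is the whole panel. The SAP says it was fixed in advance that "a minimum I-CVI of 0.75 would be required to indicate acceptable consensus of content validity", "with a minimum median score of 4". The section is in the past tense and reads the Round 2 medians together with the qualitative comments.

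**The concern.** A cut-off has meaning only on the scale for which it was set. The only scale the protocol describes has nine points; the SAP's threshold is expressed out of six. Neither document mentions a switch, a rescaling or a mapping between the two.

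This matters because developing the two questionnaires is the study's primary aim, and Stage 1 is the only stage at which experts rate relevance. The later stages test comprehension and factor structure and do not repeat that rating. Until the scale is known, no reported I-CVI can be interpreted. The SAP's statement that the thresholds were set in advance cannot be checked either, because the protocol records none. If a threshold of 4 was applied to 1-9 ratings, items that experts placed below the middle of the scale could be reported as content valid.

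**Working it through.** The plan has no sample-size or power figure to reproduce here. The check is where the cut-off sits on each scale and how easily an item passes.

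**Inputs.** Scale 1 to 9, same task in both rounds, 6 to 10 experts (protocol). Cut-off 4 of 6, I-CVI at least 0.75, median at least 4 (SAP). *Assumption:* the six-point scale starts at 1, since the SAP gives only its maximum.

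**1. Position of the cut-off.** Midpoint = (min + max)/2; relative position = (4 − min)/(max − min).

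- On 1-6: midpoint 3.5; position 3/5 = 60%; 3 of 6 categories count as endorsement. A score of 4 is above the midpoint.
- On 1-9: midpoint 5; position 3/8 = 37.5%; 6 of 9 categories count. A score of 4 is below the midpoint.
- If the six-point form ran from 0 to 6 instead: midpoint 3; position 4/6 = 66.7%. A score of 4 is still above the midpoint.

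**2. Worked item on 1-9.** Eight experts all rate 4. I-CVI = 8/8 = 1.00 and median = 4, so both criteria are met with every rating below the midpoint. The median rule gives no further protection: once at least 75% of ratings are 4 or more, the median must be at least 4.

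**3. Translating the cut-off.** The point on 1-9 at the same relative position as 4 on 1-6 is 1 + 8 × 3/5 = 5.8, so the nearest whole number is 6.

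**4. Illustrative pass rates.** The number of endorsements needed is r = ceil(0.75n). With ratings uniform at random, the chance of passing is P(X ≥ r) for X ~ Binomial(n, p), where p is the share of categories at or above the cut-off.

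| n | r | ≥4 on 1-6 (p = 3/6) | ≥4 on 1-9 (p = 6/9) | ≥6 on 1-9 (p = 4/9) |
|---|---|---|---|---|
| 6 | 5 | 0.109 | 0.351 | 0.066 |
| 7 | 6 | 0.063 | 0.263 | 0.033 |
| 8 | 6 | 0.145 | 0.468 | 0.083 |
| 9 | 7 | 0.090 | 0.377 | 0.046 |
| 10 | 8 | 0.055 | 0.299 | 0.025 |

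Examples: n = 8 with p = 6/9 gives (28 × 64 + 8 × 128 + 256)/6561 = 3072/6561 = 0.468. For n = 10 with p = 1/2 it is (45 + 10 + 1)/1024 = 56/1024 = 0.055.

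Uniform rating is a device for comparing the strictness of the three rules. It is not a model of how experts rate.

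**The case against.** The best defence is that a six-point form was actually administered and the protocol was not updated. The SAP is written in the past tense, spells out six as the maximum, and gives a cut-off and a median that fit that maximum. On that reading 4 is above the midpoint and the rule is sound. This stands as a plausible reading. It does not settle the matter, because neither document says that the scale changed, when, or why.

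A reader might infer that items rated below the midpoint did pass, or necessarily would. The documents do not support that: it requires the cut-off of 4 to have been applied to 1-9 ratings, and no text says it was.

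A reader might also infer that this rule alone decided which items went to patients. The SAP says that medians were considered with all the qualitative feedback and that refinements followed. It does not say that failing items were dropped or passing items kept automatically. Two rounds of patient interviews and the communality and loading criteria come later. They limit the harm but do not replace the experts' relevance ratings.

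Finally, the random-rating figures do not predict how many items would change status. The initial items came from qualitative research and literature review, so random rating is unrealistic.

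**Conclusion.** The contradiction is established: a 1-9 scale in the protocol for both rounds, a cut-off out of six in the SAP, and no link between them. At least one document must be corrected.

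The consequence depends on which scale was administered, and the documents do not establish that. If it was 1-9, the cut-off sits at 37.5% of the range, below the midpoint, and a unanimous rating of 4 passes both criteria. The rule is then much weaker than on 1-6: 26-47% against 5-14% of randomly rated items would reach I-CVI 0.75 with 6 to 10 experts. If it was 1-6, the rule is coherent and the fault is an unrecorded departure from the protocol.

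A stricter cut-off, such as 7 on 1-9, may be tempting, but it appears in neither document. The SAP's own rule translates to 5.8, that is 6. The translation assumes a linear mapping and a lower anchor of 1 on the six-point form.

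**What to change.** State in the SAP which scale was administered in Round 1 and in Round 2. If it differed from the protocol, say when it changed relative to the setting of the thresholds. Give the I-CVI cut-off and the minimum median explicitly on that scale.

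- **If 1-9 was used:** define endorsement as a rating of 6 or more and set the median rule at 6. Recompute every relevance and clarity I-CVI from the ratings already held, and list the items whose status changes. A cut-off of 7 may be added as an optional sensitivity analysis. State openly that the corrected cut-off was set after the ratings were collected, as a translation of the 4-of-6 rule.
- **If 1-6 was used:** keep the cut-off and correct the protocol through a dated deviation note, so that the record of the planned 9-point scale and its justification is preserved.

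The cost is wording in two documents and, in the first case only, a recount of ratings from 6 to 10 experts. Some items might then lose their content-valid status; the documents give no basis for saying how many.
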